9.3.13 Post-surgical ophthalmological adverse events

Patients who develop post-surgical complications such as ocular inflammation and raised IOP should be treated according to local standard of care procedures.

Intraocular inflammation worsening during the course of treatment with the protocol defined anti-inflammatory regimen (see [Section 9.2.2](#) Intraocular Injection) or persisting or occurring after the completion of the protocol defined anti-inflammatory regimen must be recorded as a post-surgical ophthalmological adverse event.

In this setting the treatment and follow-up of the patient will be at the discretion of the investigator, guided by the severity and longevity of the inflammation, in an effort to minimize the risk of loss of visual function as a result of the ongoing inflammatory process. In the situation where the intraocular inflammation is clinically worsening the presence of an intraocular infection should be excluded.

Treatment with high dose, oral corticosteroids (1 mg/kg/day for patients ≥ 50 kg; 0.5 mg/kg/day for patients < 50 kg; maximum dose not to exceed 80 mg/day for children < 16 years) is recommended for any patient manifesting worsening intraocular inflammation (eg, $\geq 2+$ for anterior chamber cells, ≥ 2 vitreous haze and/or cells, the presence of vitreous snowballs or retinal vasculitis). In such cases, the oral corticosteroids should be continued until the ocular inflammation is resolved and then tapered as appropriate.

Raised IOP greater than 30 mmHg must be recorded as a post-surgical adverse event and may be treated with IOP lowering drops with the patient reviewed within a week. If the IOP remains greater than 25 mmHg another pressure lowering drop will be added and the patient reviewed again within a week. This sequence will be repeated until the IOP remains below 25 mmHg. For increases in IOP occurring while the patient is receiving topical steroids per the recommended protocol defined anti-inflammatory regimen, consideration may be given to reducing the frequency of the topical steroids if the intraocular inflammation is controlled.

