11 OBLIGATIONS OF THE INVESTIGATOR REGARDING SAFETY REPORTING

11.1 ADVERSE EVENT DEFINITION

An adverse event (AE) is any untoward medical occurrence in a patient that develops or worsens in severity during the conduct of a clinical study of a pharmaceutical product and does not necessarily have a causal relationship to the investigational product. This can, therefore, be any unfavorable and unintended physical sign, symptom, or laboratory parameter that develops or worsens in severity during the course of the study, whether or not considered related to the investigational product.

All AEs must be described in the appropriate section of the CRF and their seriousness and putative relationship (causality) to the study medication and/or protocol procedures noted. Adverse events are recorded following signature of the informed consent; this is to ensure that any adverse events associated with the screening procedures are captured.

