11.6 GENERAL GUIDELINES FOR REPORTING ADVERSE EVENTS

- All AEs, regardless of seriousness or relationship to IMP, spanning from the signature of the informed consent form until the end of the study as defined by the protocol for that patient, are to be recorded on the corresponding page(s) or screen(s) of the CRF.
- Whenever possible, diagnosis or single syndrome should be reported instead of symptoms. The investigator should specify the date of onset, intensity, action taken with respect to IMP, corrective treatment/therapy given, additional investigations performed, outcome, and his/her opinion as to whether there is a reasonable possibility that the AE was caused by the IMP or by the study procedure(s).
- The investigator should take appropriate measures to follow all AEs until clinical recovery is complete and laboratory results have returned to normal, or until progression has been stabilized, or until death, in order to ensure the safety of the patients. This may imply that observations will continue beyond the last planned visit per protocol, and that additional investigations may be requested by the monitoring team up to as noticed by the Sponsor. Patients who experience an ongoing SAE or an AESI, at the pre-specified study end-date, should be followed until resolution, stabilization, or death and related data will be collected. The duration of post-study follow-up and reporting of AEs will be until recovery.
- When treatment is prematurely discontinued, the patient's observations will continue until the end of the study as defined by the protocol for that patient.

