13.4 SAFETY ENDPOINTS

13.4.1 Adverse Events

The number and percentage of patients with treatment emergent adverse events (ie, started or increased in severity after the patient received study treatment and includes abnormal lab results, ECGs etc.) will be summarized. The adverse events recorded prior to SAR421869 administration will not be summarized and will be separated from the adverse events that are recorded post SAR421869 administration in the final listings.

An overall summary will include the number and percentage of patients with:

- A fatal AE (death).
- At least one serious AE.
- At least one severe AE.
- At least one related AE.
- Without any AEs.

- An additional table will show the number and percentage of patients with treatment emergent adverse events broken down by System Organ Class, High Level Term and Preferred Term. Related AEs will be summarized separately.
- Specific grouping will be done for ocular events that are inflammatory in nature.

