17 APPENDICES

Appendix A Ocular Inflammation grading

Slit-lamp examination will be performed throughout the study to monitor for ocular inflammation. In addition, BCVA, other clinical examination and the results of other investigations such as FA may also assist in the evaluation.

The objective assessment of inflammation will comprise separate assessment of the anterior segment, vitreous and fundus. Active inflammation only will be assessed and any signs of previous inflammation (eg, premacular fibrosis, healed old choroidoretinal scars will not be included in the evaluation of the severity score.)

Prelimbal injection will be noted as present or absent, no attempt will be made to assign a severity score. Anterior chamber findings will be graded according to cell numbers and the intensity of flare using the widest slit beam and luminescence of the slit lamp (Pigmented cells and red blood cells will not be counted). See Table 1.

Table 1 - Slit-Lamp Examination Grading of Anterior Chamber Cells and Flare

Grade	Cells / field (Field size is 1mm x1mm)
0	<1 cells/field
0.5+	1-5
1+	6-15
2+	16-25
3+	26-50
4+	>50

Grade	Description of flare
0	None
1+	Faint
2+	Moderate (iris and lens detail clear)
3+	Marked (iris and lens detail hazy)
4+	Intense (fibrin or plastic aqueous)

(The standardization of uveitis nomenclature [SUN] working group. J Ophthalmol 2005;140:509-516) (46)

Vitreous haze, if present is the most reliable sign of intraocular inflammation and the main indicator of response to treatment. Vitreous haze is can be determined using fundoscopy (indirect ophthalmoscopy). The scoring system is given in Table 2 but it is important to note that the grading system is subjective only and media, corneal or lens opacities may significantly influence the score.

Table 2 - Grading of Vitreous Haze

Grade	Description	Clinical findings
0	nil	none
1	minimal	posterior pole clearly visible
2	mild	posterior pole detail slightly hazy
3	moderate	posterior pole detail very hazy
4	marked	posterior pole detail barely visible
5	severe	fundal detail not visible

Inflammation will be assessed by slit-lamp examination and fundoscopy at all study visits. The inflammation grading data will be reported and monitored by the DSMB.

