7.3.1 Adverse Events

AEs will be coded using MedDRA® (last version available at time of database lock). All reported events for all patients with cohort, event description, event date, resolution date, severity, outcome, relatedness, SAE indication, duration, High Level Term (HLT), System Organ Class (SOC), and Preferred Term (PT) will be listed. Specifically, AEs prior to treatment, treatment emergent adverse events (TEAEs), (i.e., started or increased in severity after the patient receives IMP, including abnormal lab results, ECG, etc.) and TEAEs of special interest will be listed separately. An overall summary table of TEAEs will also be provided that includes the number and percentage of TEAEs and patients with at least one TEAE in each dose cohort with:

- A fatal AE (death)
- At least one serious AE
- At least one severe AE
- At least one AE related to IMP
- At least one TEAE related to procedure
- Without any AEs

In addition, tables will present both the number and percentage of TEAEs and patients with TEAEs by SOC, HLT, PT, severity and cohort. Adverse events of special interest (AESI), detailed in the protocol, will be summarized by SOC, HLT, PT, severity and cohort. AESIs will be indicated, where appropriate in the patient profile listing of AEs. AEs related to the IMP and serious adverse events (SAEs) will be indicated in the AE listing and described in detail in the body of the report. Specific grouping will be done for events inflammatory in nature in the eye. Summary tables will be presented both with the inflammatory events grouped and without the events grouped. All events with the following preferred terms will be considered inflammatory in nature in the eye:

- Anterior chamber cell
- Anterior chamber inflammation
- Choroidal effusion
- Conjunctivitis
- Eye inflammation
- Eye discharge
- Keratitis

- Macular oedema
- Subretinal fluid
- Uveitis
- Vitreous floaters

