7.3.3 Ocular Inflammation

The grading system of ocular inflammation can be found in Appendix A of the study protocol. The inflammatory grades will be treated as ordinal variables and plotted by patient over time. Scores for ocular inflammation, including anterior chamber cells, flare (slit lamp examination) and vitreous cells, haze (indirect ophthalmoscopy) and macular edema, will be listed by eye and shown graphically similar to the other ophthalmic endpoints. Summary counts for the number of 'step-up' and 'step-down' changes in the inflammation scale in the study eye may be tabulated by cohort and visit. Clinically important changes (i.e., ≥ 2 step change) as observed in slit lamp examination and/or indirect ophthalmoscopy at any point from Day -28 to Week 48 will be indicated and listed where appropriate.

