		PT1										
		PT2										
All\												

Tables 3E and 3F summarize TEAEs and patients with at least one TEAE by MedDRA SOC, HLT, PT, severity and cohort, with all inflammatory events grouped into a single PT.

**Table 3E: Number of TEAEs by MedDRA SOC, HLT, PT, Severity and Cohort with Inflammatory Events Grouped
(Event-based Counts)**

SYSTEM ORGAN CLASS (SOC)	HIGH LEVEL TERM (HLT)	PREFERRED TERM (PT)	COHORT									
			1		2		3		4		All Cohorts	
			Mild	Mild	Moderate	Mild	Moderate	Severe	Mild	Moderate	Mild	Moderate
SOC1	HLT1	PT1										
		PT2										

		COHORT										All Cohorts			
		1	2	3				4		All Cohorts					
		Mild	Mild	Moderate	Mild	Moderate	Severe		Mild	Moderate	Mild	Moderate	Severe		
SOC2	HLT1														
	PT1														
	PT2														
All															

Table 3F: Number of Patients Experiencing TEAEs by MedDRA SOC, HLT, PT, Severity and Cohort with Inflammatory Events Grouped (Patient-based Counts)

(Note that if more than one event in each category is reported for a single patient, the most recent event of maximum severity is counted.)

			COHORT										All Cohorts			
			1	2	3				4		All Cohorts					
			Mild	Mild	Moderate	Mild	Moderate	Severe		Mild	Moderate	Mild	Moderate	Severe		
SYSTEM ORGAN CLASS (SOC)	HIGH LEVEL TERM (HLT)	PREFERRED TERM (PT)														
SOC1	HLT1	PT1														
		PT2														
SOC2	HLT1															
	PT1															
	PT2															
All																

Tables 3G and 3H summarize patients with at least one TEAE related to IMP and procedure, respectively, by MedDRA SOC, HLT, PT, severity and cohort.

Table 3G: Number of TEAEs Related to IMP by MedDRA SOC, HLT, PT, Severity and Cohort (Patient-based Counts)

SYSTEM ORGAN CLASS	HIGH LEVEL TERM (HLT)	PREFERRED TERM (PT)	COHORT								All Cohorts	
			1		2		3		4			
			Mild	Mild	Mild	Moderate	Mild	Moderate	Severe	Mild	Moderate	Severe
SOC1	HLT1	PT1										
		PT2										
SOC2	HLT1											
		PT1										
		PT2										
All												

Table 3H: Number of TEAEs Related to Procedure by MedDRA SOC, HLT, PT, Severity and Cohort (Patient-based Counts)

SYSTEM ORGAN CLASS	HIGH LEVEL TERM (HLT)	PREFERRED TERM (PT)	COHORT								All Cohorts	
			1		2		3		4			
			Mild	Mild	Mild	Moderate	Mild	Moderate	Severe	Mild	Moderate	Severe
SOC1	HLT1	PT1										
		PT2										

COHORT												
SOC2	HLT1	1		2		3		4		All Cohorts		
		Mild	Mild	Moderate	Mild	Moderate	Severe	Mild	Moderate	Mild	Moderate	Severe
SOC2	HLT1											
	PT1											

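### The closed list of preferred terms that defines ocular inflammatory events omits vitreous cells, haze and snowballs, flare and retinal vasculitis, so memo Table 3E could miss such an event (minor)

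*SAP*

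**What the plan says.** Protocol 13.4.1 states the aim without a term list: "Specific grouping will be done for ocular events that are inflammatory in nature". SAP 7.3.1 supplies the rule: "All events with the following preferred terms will be considered inflammatory in nature in the eye". Eleven terms follow: *Anterior chamber cell, Anterior chamber inflammation, Choroidal effusion, Conjunctivitis, Eye inflammation, Eye discharge, Keratitis, Macular oedema, Subretinal fluid, Uveitis* and *Vitreous floaters*. The list is not introduced as a set of examples, and no step is given for judging terms outside it.

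Elsewhere the documents say what they regard as ocular inflammation:

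- SAP 7.3.3 names what is scored: "Scores for ocular inflammation, including anterior chamber cells, flare (slit lamp examination) and vitreous cells, haze (indirect ophthalmoscopy) and macular edema".
- Protocol 9.3.13 illustrates worsening intraocular inflammation with anterior chamber cells, vitreous haze and/or cells, and "the presence of vitreous snowballs or retinal vasculitis".
- Protocol Appendix A grades anterior chamber cells, flare and vitreous haze, and says of the last: "Vitreous haze, if present is the most reliable sign of intraocular inflammation and the main indicator of response to treatment".

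The memo of 30 August 2019 attached to the SAP sets the final outputs. Its Table 3E counts patients with inflammatory treatment-emergent events by MedDRA level and cohort. The memo gives no new term list.

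**The concern.** Membership depends on the coded term alone. If an event that the protocol regards as ocular inflammation is coded to a term outside the 11, the inflammatory table omits it, however clear the clinical picture. The gap lies mainly in the back of the eye. The anterior chamber has two terms, and the surface of the eye has *Conjunctivitis*, *Keratitis* and *Eye discharge*. The only vitreous term is *Vitreous floaters*, and there is no term for retinal vessels.

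Safety is the primary objective, and ocular inflammation is prominent in it. Unresolving inflammation is a study stopping criterion (protocol 8.4), severe or persistent inflammation is a dose-limiting toxicity (8.5), and two serious uveitis cases, one of them in this study, led to the glucocorticoid regimen in Amendment 8. A reader of the final report will look to the inflammatory table for the overall rate.

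**Working it through.** The plan states no figure to reproduce. The check compares the signs that the documents call ocular inflammation with the 11 listed terms.

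| Sign | Treated as ocular inflammation in | Listed term of that name | Scored under SAP 7.3.3 |
|---|---|---|---|
| Anterior chamber cells | SAP 7.3.3; protocol 9.3.13; Appendix A | *Anterior chamber cell* | yes |
| Macular edema | SAP 7.3.3 | *Macular oedema* | yes |
| Flare | SAP 7.3.3; Appendix A | none | yes |
| Vitreous cells | SAP 7.3.3; protocol 9.3.13 | none | yes |
| Vitreous haze | SAP 7.3.3; protocol 9.3.13; Appendix A | none | yes |
| Vitreous snowballs | protocol 9.3.13 | none | no |
| Retinal vasculitis | protocol 9.3.13 | none | no |

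**Could a broader listed term catch the last five?** Protocol 11.6 says: "Whenever possible, diagnosis or single syndrome should be reported instead of symptoms". An event reported as a diagnosis may be coded to *Uveitis*, *Eye inflammation* or *Anterior chamber inflammation*, and would then be counted. *Anterior chamber inflammation* can fairly be read as covering flare. Two things limit this. The instruction is qualified, and the list itself works partly at sign level: it has *Anterior chamber cell* beside *Anterior chamber inflammation*. Retinal vasculitis is also a diagnosis in its own right, so the instruction does not steer it to a listed term.

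**Where else would an omitted event appear?** In the memo's tables it would be in the overall patient table (3B) and the listing (3I) and, where it qualifies, in the special-interest (3C, 3J), serious (3D, 3K), IMP-related (3F) and procedure-related (3G) outputs. Protocol 11.5 makes an event with a rise of more than two steps in anterior chamber cells and flare, or in VH (read here as vitreous haze), an event of special interest. That criterion does not mention vitreous cells, snowballs or vasculitis, although other ocular criteria in 11.5 could apply to them. Tables 3Q-3S tabulate changes in the inflammation grades in the study eye.

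**Size if it happens.** The memo's adverse event shell has N=3 per cohort and N=9 overall. One patient whose only inflammatory event carries an unlisted term changes

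- the cohort rate by 1/3 = 33.3 percentage points;
- the overall rate by 1/9 = 11.1 percentage points.

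The documents give no basis for estimating how many such patients there are.

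**The case against.** The strongest reply is that the protocol already directs how these events are recorded. Sections 9.2.2 and 9.3.13 require intraocular inflammation that worsens on the regimen, or persists or appears after it, to be recorded as an adverse event. The vitreous signs and vasculitis appear there as examples of worsening inflammation, not as proposed event terms. An event recorded as intraocular inflammation would plausibly fall under a listed term. Which dictionary terms exist for each sign, and how the coders would use them, cannot be seen in the documents. This stands, and it is why the omission is possible and not established. It does not remove the case of an isolated sign or of retinal vasculitis.

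A reader might infer more than the documents support, in four ways:

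- *That most inflammation would be missed.* By name, 3 of the 5 signs in SAP 7.3.3 are unlisted, 4 of the 5 in protocol 9.3.13, 5 of 7 pooled, and 6 of 8 if the prelimbal injection noted in Appendix A is added. The fraction depends on which sections are pooled and counts names, not events. It does not measure undercounting.
- *That the SAP misapplies protocol 13.4.1.* The SAP is version 2 of 22 July 2016. The grouping sentence came with Amendment 8, approved in August 2018. The list predates the sentence. What can be said is that the 2019 memo, later than both, did not revisit it.
- *That inflammatory events will be collapsed into one line.* SAP 8.3.1 describes Tables 3E and 3F "with all inflammatory events grouped into a single PT", but the memo replaces those shells for the final outputs, and its Table 3E is by preferred term.
- *That listing subretinal fluid without condition inflates the count, because every treated eye receives a subretinal bleb.* Only adverse events enter the table, and protocol 11.1 sets the bar: "An adverse event (AE) is any untoward medical occurrence in a patient that develops or worsens in severity". None of the 11 terms carries a condition, and with preferred-term rows a reader can recount without it. That is a matter of presentation.

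**Conclusion.** The point holds as a minor one. The closed list leaves out events coded as flare, vitreous cells, vitreous haze, vitreous snowballs or retinal vasculitis, which the documents elsewhere treat as ocular inflammation. The remaining exposure is an event coded as an isolated vitreous sign or as retinal vasculitis. The case is clearest for snowballs and vasculitis, which are not among the scores in SAP 7.3.3 either.

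The consequence is an inflammatory count in memo Table 3E that may be too low. It is confined to that descriptive table among the final outputs and may be zero. No test, stopping rule or dose decision is tied to the count, and no event disappears from the report.

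This rests on two assumptions: that the list in SAP 7.3.1 still governs memo Table 3E, since the memo offers no other; and that at least some of these signs could be coded to terms outside the list.

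**What to change.** Before database lock, extend the list in SAP 7.3.1 to the preferred terms that the coders assign to anterior chamber flare, vitreous cells, vitreous haze or vitritis, vitreous snowballs and retinal vasculitis. Keep all 11 existing terms. Print the final list as a footnote to memo Table 3E. If lock has passed, SAP 1.0 already provides for describing the departure in the final study report.

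The cost is a longer term list and one footnote, with no new data. The downside is that the reported inflammation rate may rise slightly.

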7.3.2 Best-Corrected Visual Acuity (BCVA)

BCVA (Early Treatment Diabetic Retinopathy Study [ETDRS] letters read) will be listed by visit and eye. BCVA for all patients' study eye and fellow eye will be presented graphically by visit and cohort. Mean changes in BCVA by visit and cohort will be summarized in a table and graph by cohort and visit.

7.3.3 Ocular Inflammation

The grading system of ocular inflammation can be found in Appendix A of the study protocol. The inflammatory grades will be treated as ordinal variables and plotted by patient over time. Scores for ocular inflammation, including anterior chamber cells, flare (slit lamp examination) and vitreous cells, haze (indirect ophthalmoscopy) and macular edema, will be listed by eye and shown graphically similar to the other ophthalmic endpoints. Summary counts for the number of 'step-up' and 'step-down' changes in the inflammation scale in the study eye may be tabulated by cohort and visit. Clinically important changes (i.e., ≥ 2 step change) as observed in slit lamp examination and/or indirect ophthalmoscopy at any point from Day -28 to Week 48 will be indicated and listed where appropriate.

7.3.4 Intraocular Pressure (IOP)

The IOP for each visit will be measured using applanation tonometry. IOP will be listed by visit and eye. IOP for all patients' study eye and fellow eye will be presented graphically by visit and cohort. Mean changes in IOP by visit and cohort will be summarized in a table and graph by cohort and visit.

Clinically important changes and the number of individuals with $IOP \geq 25$, ≥ 30 , and ≥ 35 mmHg at any point from Day -28 to Week 48 will be tabulated by cohort and visit.

7.3.5 Optical Coherence Tomography (OCT)

Central macular thickness, subretinal fluid, macular volume and other architectural features will be measured by OCT. Individual values of macular thickness (in the central sub-field) and macular volume will be listed and illustrated graphically similar to the other ophthalmic endpoints. Macular thickness and volume will be listed by visit and eye. Macular thickness and volume for all patients' study eye and fellow eye will be presented graphically by visit and cohort. Mean changes in macular thickness and volume by visit and cohort will be summarized in a table and graph by cohort and visit.

